- A quality improvement study by Srinivasan et al demonstrated that 58% of patients admitted to hospital with bronchiolitis over a 4-month period received nasogastric hydration¹⁸.

The safety of nasogastric fluids has been assessed in several studies

• The retrospective cohort study by Oakley et al reported an adverse event rate of 27.4% in those that received nasogastric fluids, with 21.9% of these being desaturations, 5.5% being apnoeas (with one patient requiring caffeine), 2.7% being bradycardias (with two patients

requiring inotropic support) and no aspiration events recorded ¹⁹. 12.3% of patients receiving nasogastric fluids went on to require intravenous fluids. 19.9% of patients receiving nasogastric fluids required intensive care unit admission ¹⁹. The subsequent randomised control trial by Oakley et al. demonstrated a 2% incidence of bradycardia and a 1% incidence of apnoeas, in patients receiving nasogastric fluids ³. There were no episodes of epistaxis or aspiration in any of the infants studied during their time in hospital ³. 13% of infants receiving nasogastric fluids went on to require intravenous fluids and 8.5% of patients receiving nasogastric fluids required intensive care unit admission. The difficulty with the adverse events reported in this study is that it is unclear whether the adverse events reported were directly related to the nasogastric fluids used or related to the natural history of the patient's bronchiolitis.

- The study by Kugelman et al did not demonstrate any cases of aspiration in those receiving nasogastric fluids and did not demonstrate any worsening of patients' respiratory status¹³.
- A case study by Unger & Cunningham did not report any complications related to nasogastric feeding¹⁴.
- The quality improvement study by Srinivasan et al. reported no aspiration events in patients receiving nasogastric fluids¹⁸.
- A pilot study by Sammartino et al. (2002) described 37 patients during a seasonal epidemic of bronchiolitis that required hydration support⁵. The majority of patients tolerated nasogastric fluids well, with only 2 patients deteriorating (subsequently requiring intravenous fluids), thought to be secondary to the natural history of the illness⁵.

Differing regimes for nasogastric fluids have been utilised in previous studies.

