 - We have defined this adverse event as when a patient experiences a sudden increase in any of the following that occurs persistently during, or within an hour after the patients nasogastric fluid regime has commenced
 - Heart rate >20 above baseline
 - Respiratory Rate > 10 above baseline
 - Work of breathing
 - Oxygen requirement

Both nasogastric fluid regimes are essentially treatment as usual, so we expect that the study as a whole poses no foreseeable additional risk to patients. We will still perform safety analysis on the pilot data collected.

We do not anticipate any significant difference in safety between the interventions. If we do detect a significant difference in safety, we will have procedures in place to address this for the subsequent larger study.

There is no evidence in the literature to suggest that patients receiving nasogastric fluids are at risk of a serious adverse event (SAE), such as

- death during the study period
- electrolyte disturbance causing seizure
- Any other event not mentioned above that is life threatening or jeopardises the patient or requires medical or surgical intervention

We will endeavour to manage any serious adverse events with the following practice:

- SAEs need to be reported within 24 hours by telephone to the local site investigator.
- The local investigator must report the SAE to their local ethics committee within 48 hours (or in accordance with local ethics committee regulations).
- The local investigator must also report SAEs to the principal investigators who will report the event to the Data Monitoring Committee chairman.
- The principal investigator will also report the SAE to all Ethics Committees and other regulatory bodies involved in the trial as per regional regulatory requirements.
- SAEs will also be reported to the consultant of the child's treating team. The medical consultant will initiate appropriate management and inform the family if the family is not already aware of the event. This reporting is the responsibility of the site investigator

g. Participant Withdrawal Procedures

Parents/guardians of any patient enrolled in the trial are able to withdraw their consent at any point after it is initially obtained either verbally or through written means. At the point of withdrawal of consent, the treating clinician will determine the course of ongoing therapy for the patient in discussion with the patients' parent/guardian as per normal practice.

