As this is a pilot trial, we aim to assess a range of outcomes to determine the feasibility of progressing with a subsequent larger randomized control trial

- As part of this pilot trial we aim to recruit more than 80% of eligible patients, determine the
 appropriateness and variance of our primary outcome and to further help us determine the
 sample size needed for our subsequent randomised control trial
- Estimation of our recruitment rate
- Retention rates for those in the intervention groups
- Determine the incidence of adverse events
- Auditing the completeness of data reporting
- The primary investigator will collect field notes and reflections on the study process, including aspects such as
 - o Identifying the willingness of clinicians to recruit patients
 - o Estimation of cost and resources
 - o Identification of any major issues with the study process

As part of this pilot we are also collecting data for all the intended outcomes for the larger trial to fully test the study procedures and data collection but will not use them for formal analyses. These other outcomes include:

- Time taken for the patient to return to adequate oral feeding after the introduction of nasogastric fluids. This is the primary outcome for our subsequent larger trial.
- Length of stay (in hours).
- The incidence of adverse events that may be attributed to nasogastric fluid therapy, including
 - Vomiting
 - o Pulmonary aspiration of nasogastric fluids
 - o Worsening of the patients respiratory status
- The number of infants requiring re-instatement of nasogastric fluids after nasogastric fluids are initially ceased
- The number of infants requiring a change from Nasogastric to intravenous fluid hydration
- The duration of supplemental oxygen requirement
- The need for admission to an Intensive Care Unit

i. Data Collection

A research assistant will be responsible for collecting relevant demographic and outcome data. Reidentifiable, coded patient information data will initially be recorded by the research assistant onto NOBRO study source document. The research assistant will then input this data into an Excel Spreadsheet. This spreadsheet will be password-protected and be located on a dedicated computer that only the research assistant has access to.

Following merging, identifiable data shall be made non-identifiable. The NOBRO study source documents will also be stored in a locked drawer in the research assistant's office.

k. Data Storage and Confidentiality

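### The named adverse-event definitions give non-severe apnoea and bradycardia no route and count desaturation only through oxygen requirement, and the statement on serious-event risk conflicts with the Background

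*Protocol*

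**What the plan says.** Section 3.f (Risk Mitigation Procedures) lists vomiting, pulmonary aspiration and a worsening of respiratory status believed to be due to the feeding regime. The first two are graded by CTCAE. The third is defined as "a sudden increase in any of the following that occurs persistently during, or within an hour after" the start of the regime. Its four items are "Heart rate >20 above baseline", "Respiratory Rate > 10 above baseline", work of breathing, and "Oxygen requirement".

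Section 3.i (Outcome Measures) makes adverse-event incidence a pilot outcome. Among the data collected for the later trial it lists "The incidence of adverse events that may be attributed to nasogastric fluid therapy, including" the same three events.

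Section 1 (Background) describes what earlier studies saw in infants on nasogastric fluids. In a retrospective cohort the adverse-event rate was 27.4%. The protocol breaks this down as 21.9% desaturations, "5.5% being apnoeas (with one patient requiring caffeine), 2.7% being bradycardias (with two patients" needing inotropic support), with no aspiration. The later randomised trial is reported as showing a "2% incidence of bradycardia and a 1% incidence of apnoeas", again with no aspiration.

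Section 3.f then states: "There is no evidence in the literature to suggest that patients receiving nasogastric fluids are at risk of a serious adverse event (SAE"). The examples that follow end with a catch-all for any other event that threatens life, puts the patient in jeopardy or needs medical or surgical intervention.

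**The concern.** The safety outcome does not match the safety evidence that the protocol itself cites. Aspiration, which neither of the two main cited studies observed, has a graded definition. Apnoea, bradycardia and desaturation, which were observed, have none. The one definition that might have caught them looks only for rises, and only for rises that persist.

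Two things are at stake. First, a pilot that follows these definitions will undercount cardiorespiratory events, and the same definitions may pass unchanged into the larger trial. That matters here because the Background cites a local guideline's worry that gastric distension from bolus feeds may worsen respiratory symptoms, so these events bear on the comparison the larger trial will make. Second, the sentence on SAE risk tells an ethics committee something that the Background does not bear out.

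**Working it through.** The protocol derives no figure on this point, so there is none to reproduce. The check is a comparison of the text, followed by arithmetic to size the gap.

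**Step 1: each reported event against the named definitions.**

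- Bradycardia is a fall in heart rate. The heart-rate criterion is a rise of more than 20, so it is not met.
- Apnoea is a pause in breathing. The respiratory-rate criterion is a rise of more than 10, so it is not met. A brief pause would also fail the persistence condition.
- Desaturation has no saturation criterion. It counts only if it leads to a higher oxygen requirement.
- None of the three is named in 3.f or 3.i.

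**Step 2: the SAE sentence against the Background.** The catch-all in 3.f includes events that need medical intervention. One infant with apnoea needed caffeine and two with bradycardia needed inotropic support. Those cases fit the protocol's own SAE wording, so the flat denial of any evidence does not stand beside them.

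**Step 3: size.** Inputs: n = 30 (Synopsis; Data Analysis and Statistical Considerations) and the rates in the Background. Expected number of infants = 30 × p; chance of at least one = 1 − (1 − p)^30, treating infants as independent.

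| Source and event | p | 30 × p | Chance of at least one |
|---|---|---|---|
| Randomised trial, apnoea | 0.01 | 0.3 | 1 − 0.99^30 = 26% |
| Randomised trial, bradycardia | 0.02 | 0.6 | 1 − 0.98^30 = 45% |
| Cohort, apnoea | 0.055 | 1.65 | 1 − 0.945^30 = 82% |
| Cohort, bradycardia | 0.027 | 0.81 | 1 − 0.973^30 = 56% |
| Cohort, desaturation | 0.219 | 6.57 | over 99% |

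The protocol gives no desaturation rate for the randomised trial.

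**Step 4: the cohort denominator.** The table reads the cohort figures as percentages of patients. The Background's wording literally makes them shares of the 27.4%. On that reading:

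- apnoea: 0.055 × 0.274 × 30 = 0.45
- bradycardia: 0.027 × 0.274 × 30 = 0.22
- desaturation: 0.219 × 0.274 × 30 = 1.8

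The three percentages sum to 21.9 + 5.5 + 2.7 = 30.1. That is slightly above 27.4, as overlapping events in the same patients would give, and far from 100. The per-patient reading is the more plausible, but both are shown.

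**The case against.** A reader might infer that these events cannot be recorded at all. The documents do not support that. A severe apnoea or bradycardia would fall under the SAE catch-all. Intensive care admission, duration of supplemental oxygen, and type and duration of respiratory support are all collected. Both adverse-event lists are worded as open. What remains is that events below SAE level are neither defined nor named for collection.

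A reader might also take the cohort rates as a forecast for this pilot. They are not one. The Background says the cohort was under 2 months old, and it reports 19.9% intensive care admission. The pilot enrols up to 12 months. It excludes infants on more than 2 L/kg of high flow, on mask ventilation or intubated, and those strongly suspected of needing escalation within 24 hours. The randomised trial, at 2–12 months, is closer in age to most of the eligible range, and at its rates zero events of each kind is the likelier result.

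Nor should much be made of a lost comparison between arms. The pilot has 30 infants and plans no formal hypothesis testing, so extra fields would not make the arms comparable on rare events. Section 3.f does promise a safety analysis, however, and it needs usable counts.

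On the SAE sentence, the Background says of the randomised trial that it is unclear whether events arose from the fluids or from the illness. That supports saying causation is not established. It does not support saying there is no evidence. The Background stands in the same document, so nothing is hidden from the ethics committee; the two passages simply disagree.

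**Conclusion.** The point holds in a limited form. Applied as written, the named definitions leave apnoea and bradycardia below SAE level uncounted, and count desaturation only when oxygen requirement rises. The gap follows from the wording and does not depend on any rate.

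Its size does depend on the rates. The trial-based figures are the better guide for most of the eligible age range: fewer than one infant expected with each of apnoea and bradycardia. The cohort-based figures are an upper range. Both assume that rates from other populations carry over. The Bedside Data Collection Form is not in the protocol, so whether it already has space for these events is unknown.

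The SAE sentence conflicts with the Background and needs rewording. Because this is a feasibility pilot without formal testing, the point is a should-fix. The main harm would be carrying an incomplete safety measure into the larger trial.

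**What to change.** In 3.f and 3.i, name apnoea, bradycardia and desaturation as recorded adverse events, collected in the same way in both arms. Record believed attribution to the feeding regime as a separate item, not as a condition for counting the event; the staff are unblinded and the Background itself calls attribution unclear. The clinical investigators should set the definitions and thresholds.

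Reconcile the SAE sentence in 3.f with the Background: state that serious events have been reported in infants receiving nasogastric fluids, and that a causal link is not established.

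The cost is a protocol wording change and a few more fields on the bedside form, with the matching staff instruction.

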If a patient is withdrawn from the study after consent has been obtained, but before randomisation occurs, baseline demographic data and outcome data will not be collected or reported on for that participant. In cases where baseline demographic data has already been collected, this information will be deleted from any health records and destroyed.

If a patient is withdrawn from the study after randomisation, no new information will be collected from the time of withdrawal but any information that was collected prior to withdraw will still be used and kept for the purpose of this study.

Parent/guardians of patients that initially decline consent to the study will be excluded from the study and will not be able to enter the study at a later point in the patient's clinical course

h. Study Procedure

Randomisation

Treating clinicians, nurses and our research assistant will identify if a patient in the Emergency Department, Childrens Inpatient Unit or Childrens Critical Care Unit with bronchiolitis that require nasogastric fluid therapy, due to poor oral feeding or concerns of dehydration.

These patients' parents or guardian will be given an information leaflet regarding the NOBRO trial, as well as a consent form to participate in the trial.

If the parent/guardian consents to the patient being enrolled in the study, the patient will undergo randomisation.

Randomisation will be performed by the patients treating nurse and witnessed by another nursing or medical staff member to minimise any randomisation bias. All nursing staff looking after patients with bronchiolitis will undergo training in how to perform the randomisation and collect outcome data.

A block randomization strategy will be employed using the ralloc command of the statistical software Stata 15. Randomizations will be provided in consecutively numbered opaque sealed envelopes.

We will employ a research assistant to assist in identifying, recruiting and randomising eligible patients, as well as helping with providing education about the NOBRO study to medical and nursing staff working in the emergency department, inpatient paediatric ward and paediatric critical care unit.

Allocation

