If the patient pulls out their nasogastric tube and the treating doctor or nurse makes a clinical decision not to replace the nasogastric tube. In this circumstance, details of the events leading to the change in feeding will be recorded on the bedside data collection form. If the patient continues of nasogastric feeds, data collection will continue on the alternate feeding regimen to assess for ongoing feed intolerance. Where NG feeds are ceased, the time that two consecutive adequate oral feeds will also be collected.

Data Collection

A research assistant will be responsible for collecting relevant demographic and outcome data.

The demographic data we will collect on patients in the study includes:

- o Age (in months)
- o If the patient was born prematurely (<37 weeks gestation)
- Sex
- Weight at admission and discharge
- Oral feeding practices pre-hospital admission (breast fed, formula fed, or both) including typical duration of normal feeds pre-hospital admission
- o Severity of bronchiolitis as defined by the patients Modified Tal Score²⁵
- Any pre-existing risk factors that could indicate more severe bronchiolitis⁶
 - History of significant preterm delivery (<32 weeks gestation)
 - Chronological age < 6 weeks
 - Congenital cardiac disease
 - Neurological or neuromuscular disorder
 - Immunodeficiency
 - Trisomy 21
 - Chronic respiratory illness including Chronic Neonatal Lung Disease (CNLD) or Cystic Fibrosis (CF)
- o Duration of illness (in days) before hospital admission
- o Respiratory support during admission (type and duration).
- o If the patient had an additional diagnosis eg. pneumonia

The research assistant will have access to (and have had training on how to use) NOBRO study Bedside Data Collection Form to record demographic and outcome measures on. The Bedside Data Collection Form will remain de-identified and only coded information will be transcribed on to the Bedside Data Collection Form.

If the patient is transferred to another hospital during their inpatient stay, outcome data will be reported for the patient up until they have been transferred out of the hospital. Any further outcome data will not be reported on for that patient in the study's results, though we will attempt to access information regarding the patients' outcome at their next hospital.

i. Outcome Measures

Outcome measures for pilot trial

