Information collected from the study will be disposed of 5 years after the youngest patients' 18th Birthday. Any electronic records relating to study data will be deleted and paper records will be placed into appropriately labelled shredding bins

I. Data Analysis and Statistical Considerations

No formal hypothesis testing will be completed, as this is a pilot study. Descriptive statistics will be used to measure the various outcomes of the trial- e.g. data completeness, % eligible patients approached, % eligible patients approached who then consented, total number of eligible patients per week. Data analysis will be done using Microsoft Excel in consultation with the biostatistician.

Data analysis in this pilot study will primarily be related to determining an appropriate sample size and analysis methods for the subsequent RCT. Data will be collected over a 2 month period during which we anticipate to recruit 30 participants based on the current bronchiolitis presentation rate.

The primary outcome measure will be time to adequate oral feeding (TAOF) as detailed above. Descriptive and graphical statistics will be used to ascertain the nature of the frequency distribution of TAOF. Understanding the nature of the distribution of TAOF will inform the most appropriate analysis method to be used in the RCT. If the distribution is normal, or can adequately be transformed to normality, the standard deviations (SDs) of TAOF in each treatment group along with means will be calculated. The SD estimates may then be used to estimate the sample size required in the RCT. The other requirement for this sample size estimation is an understanding of what the minimal clinically important difference (MCID) in TAOF is. As this is a new and specific measure, clinical members of the team will use this preliminary TAOF data to determine a consensus MCID for TAOF. Given this information, preliminary analyses will be undertaken to detect any difference, if any, in TAOF.

Similar analyses will be undertaken with respect of secondary objectives, hospital length of stay, and tolerability though these will not inform sample size. With respect to tolerability, this preliminary data will be used to assess possible tolerability indices that may be used in the main RCT.

At the end of the pilot, a qualitative judgement will be made by all investigators as to whether the it is appropriate to proceed, in line with Abbott $(2014)^{23}$:

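### Time to adequate oral feeding (TAOF) is cut off at transfer, receiving-hospital values are sought but barred from the results, and the planned means and SDs have no rule for an unfinished time

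*Protocol*

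**What the plan says.** Section 3.h (Data Collection) limits reporting after transfer: "outcome data will be reported for the patient up until they have been transferred out of the hospital". It continues: "Any further outcome data will not be reported on for that patient in the study's results", and then adds "though we will attempt to access information regarding the patients' outcome at their next hospital". The value is sought, but it may not enter the results.

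Section 3.g covers withdrawal: "If a patient is withdrawn from the study after randomisation, no new information will be collected from the time of withdrawal". Data gathered before that point are kept and used.

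Section 3.l first describes the TAOF distribution with descriptive and graphical statistics. It then plans a summary subject to a condition: "If the distribution is normal, or can adequately be transformed to normality, the standard deviations (SDs) of TAOF in each treatment group along with means". Those SDs may be used to size the main RCT, the shape of the distribution is to guide the choice of RCT analysis, and the clinical team will use the same data to agree a minimal clinically important difference. The section does not say what happens to an infant whose TAOF was not reached before transfer or withdrawal.

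One route to an unfinished time is already closed. If nasogastric feeding stops for another reason, section 3.h still follows the endpoint: "Where NG feeds are ceased, the time that two consecutive adequate oral feeds will also be collected".

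**The concern.** TAOF is a time to an event. An infant who leaves before two adequate feeds contributes only a lower bound. A plain mean and SD must either drop that infant or enter the cut-off time as though feeding had resumed then, and neither is correct in general.

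What is at stake is the main purpose of the pilot. Sections 1 and 3.i say that it is run to learn how TAOF behaves and how variable it is. Its mean, SD and shape feed the sample size, the choice of analysis and the agreed important difference for the RCT. The transfer rule discards values of this outcome that the team may actually hold. Because the pilot tests the RCT's procedures, the rule could also carry over into the larger trial.

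**Working it through.** **Inputs.** From the protocol: 30 infants expected in two months; SDs by arm if TAOF is normal or transformable; follow-up cut at transfer and withdrawal. The protocol gives no TAOF mean or SD, no transfer or withdrawal rate, and no alpha, power or target difference. The 30 is an accrual forecast, so there is no sample-size figure to reproduce. Everything below that needs such inputs is an assumption.

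**Who is cut off.** Take the neutral case of a constant hazard h of transfer or withdrawal, unrelated to the infant's recovery. An infant with true TAOF t is cut off with probability 1 − exp(−h·t). This rises with t, because a slower infant is exposed for longer. No preferential transfer of sicker infants is needed.

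**Size in the neutral case.** Assume log-normal TAOF (median 36 h), with h set so that 10% are cut off (0.10 × 30 = 3 infants), and 2,000,000 simulated infants per row. Entries are ratios to the truth. *Dropped* means the infant is excluded; *counted* means the cut-off time is entered as the event.

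| log-SD | true mean TAOF of cut-off infants ÷ overall mean | mean: dropped / counted | raw SD: dropped / counted | log SD: dropped / counted |
|---|---|---|---|---|
| 0.5 | 1.26 | 0.97 / 0.94 | 0.95 / 0.98 | 0.99 / 1.27 |
| 0.7 | 1.55 | 0.94 / 0.92 | 0.90 / 0.91 | 0.98 / 1.10 |
| 0.9 | 2.00 | 0.89 / 0.89 | 0.80 / 0.83 | 0.96 / 1.03 |

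The mean is too low in every row. The raw SD is too low, but the log-scale SD is slightly low if infants are dropped and too high if they are counted. If TAOF is instead normal (mean 48 h, SD 16 h), the raw SD is unbiased when infants are dropped and about 9% too large when they are counted.

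**Effect on the RCT size.** For a fixed difference on the same scale, the sample size goes with the square of the SD ratio. Raw scale: 0.80² = 0.64 to 0.98² = 0.96 of the size needed. Log scale: 0.96² = 0.92 to 1.27² = 1.61.

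**Compared with chance.** Under normality the 95% limits for an SD are √[(n−1)/χ²] times the estimate: 0.80 to 1.34 for n = 30, and 0.73 to 1.58 for n = 15 (one arm, assuming equal allocation). Inverted, an unbiased estimate would itself fall between 1/1.344 = 0.74 and 1/0.796 = 1.26 of the truth with 30, and between 1/1.577 = 0.63 and 1/0.732 = 1.37 with 15. The neutral-case biases lie within these ranges, with only the extreme of 1.27 at the edge for n = 30.

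**The case against.** The strongest case against acting is that few infants will be affected and the investigators will see how many. Section 3.c excludes infants transferred in and those with a clear back-transfer plan at presentation. TAOF is still collected when nasogastric feeds stop, and retention and data completeness are pilot outcomes. Section 3.l is conditional and leaves the RCT analysis open, and reporting up to transfer is compatible with censoring there. How unfinished times are handled is ordinary SAP material.

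Much of this stands. It keeps the likely effect small, and it means that treating cut-off times as complete would be an inference from silence. The withdrawal rule in section 3.g is also sound in itself; only the counting of the unfinished time needs stating. The transfer rule is different. It is written into the protocol, and an SAP that used the receiving-hospital time would contradict it.

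A reader might go further and infer that the SD will be too small and the RCT badly undersized. If exactly the slowest 5 to 10% were lost and nobody else, the raw log-normal SD would be 0.43 to 0.74 of the truth, implying 19 to 54% of the size needed. The documents do not support that reading. Nothing says that only the slowest infants leave; an infant withdrawn at hour 4 need not be a slow feeder. For log-normal data section 3.l points to the log scale, where the same extreme gives 0.84 to 0.90 (71 to 81% of the size). A loss of 10% tilted moderately towards slow feeders gives 0.98 on that scale.

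**Conclusion.** The point holds as a defect in how TAOF is followed and counted. By rule, obtainable values of the key outcome are kept out of the results, and the planned mean and SD have no provision for an endpoint not yet reached. The mean is likely to be too low. The direction of any SD bias is not fixed: too small if slow feeders are dropped, possibly too large on the log scale if cut-off times are counted as events. The apparent shape of the distribution may be distorted as well.

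The size cannot be read from the protocol. The ranges given rest on an assumed log-normal TAOF and an assumed neutral 10% loss, and they do not exceed the noise in a pilot SD by any useful margin. The reason to act is that results would depend on an unstated choice and that usable data would be thrown away, not that a large error has been shown. The change is worth making but is not critical.

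**What to change.** - **Section 3.h:** include TAOF obtained from the receiving hospital in the results for that infant.
- **Sections 3.h and 3.g:** where it cannot be obtained, and for withdrawals after randomisation, treat TAOF as right-censored at the last observation, neither dropped nor counted as an event. The stop on new collection at withdrawal stays as it is.
- **Reporting:** give the number cut off per arm, by reason.
- **Section 3.l:** describe TAOF with Kaplan-Meier curves and medians by arm. Take the SD for sizing the RCT from a method that allows for censoring, such as a log-normal or Weibull accelerated failure time fit. Keep the complete-case mean and SD as a supplement.

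The cost is a few sentences and a little analysis outside Excel. The receiving-hospital data are already to be sought. The downside is that feed records there may be less detailed, so some transferred infants will still have to be censored.
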